7.2.2. Adverse Event Intensity

The Investigator will make an assessment of intensity for each AE and SAE reported during the study and assign it to one of the following categories:

- Mild: An event that is easily tolerated by the participant, causing minimal discomfort and not interfering with everyday activities.
- Moderate: An event that causes sufficient discomfort and interferes with normal everyday activities.
- Severe: An event that prevents normal everyday activities. An AE that is assessed as severe should not be confused with an SAE. Severe is a category utilized for rating the intensity of an event; and both AE and SAE can be assessed as severe.

An event is defined as 'serious' when it meets at least one of the predefined outcomes as described in the definition of an SAE, NOT when it is rated as severe.

7.2.3. Adverse Event Relationship to Study Medication

The Investigator is obligated to assess the relationship between study treatment and each occurrence of each AE/SAE.

- A "reasonable possibility" of a relationship conveys that there are facts, evidence, and/or arguments to suggest a causal relationship, rather than a relationship cannot be ruled out.
- The Investigator will use clinical judgment to determine the relationship.
- Alternative causes, such as underlying disease(s), concomitant therapy, and other risk factors, as well as the temporal relationship of the event to study treatment administration will be considered and investigated.
- The Investigator will also consult the Investigator's Brochure and/or Product Information, for marketed products, in his/her assessment.
- For each AE/SAE, the Investigator must document in the medical notes that he/she has reviewed the AE/SAE and has provided an assessment of causality.
- There may be situations in which an SAE has occurred and the Investigator has minimal information to include in the initial report to the CRO. However, it is very important that the Investigator always make an assessment of causality for every event before the initial transmission of the SAE data to the CRO.
- The Investigator may change his/her opinion of causality in light of follow-up information and send an SAE follow-up report with the updated causality assessment.
- The causality assessment is one of the criteria used when determining regulatory reporting requirements.

7.2.4. Serious Adverse Events

An SAE is defined as any untoward medical occurrence that, at any dose:

- Results in death;
- Is life-threatening;
- Requires inpatient hospitalization or prolongation of existing hospitalization;
- Results in persistent disability/incapacity;
- Is a congenital anomaly/birth defect;
- Other situations.

7.2.5. Adverse Event Summaries

Adverse event data will be displayed in listings by participant. The number and percentage of participants with AEs will be tabulated by SOC and PT. A participant with multiple AEs within a SOC or PT will be counted once toward the total for the total for the SOC or PT.

All AEs (serious and non-serious) occurring after completion of the informed consent process and before the end of study, regardless of relationship to study drug, will be included and presented by MedDRA SOC and PT.

For TEAEs, the following will be summarized by study treatment and presented for the Safety Set.

- i. An overall summary of TEAEs, which includes:
 - a. the number and percentage of participants experiencing any TEAE
 - b. the number and percentage of participants experiencing any TEAE by strongest relationship to study medication
 - c. the number and percentage of participants experiencing any TEAE by greatest intensity
 - d. the number and percentage of participants experiencing any TESAE
- ii. the number and percentage of participants experiencing any TEAE by SOC, PT
- iii. the number and percentage of participants experiencing any TEAE by SOC, PT and the greatest intensity
- iv. the number and percentage of participants experiencing any TEAE by SOC, PT and the strongest relationship to study medication
- v. the number and percentage of participants experiencing any TEAE leading to study discontinuation by SOC and PT.

In the overall summary of AEs table, besides tabulating the number and percentage of participants, the total number of AE episodes will also be provided. If a participant has repeated episodes of a particular AE within a treatment period, all episodes will be counted in the summary table and displayed by treatment.

For displays by SOC and PT, each participant will be counted only once per SOC and PT within each treatment.

All occurrences of all AEs will be listed for each participant, grouped by treatment. The listing will contain the following information: treatment sequence, treatment, verbatim term, SOC, PT, intensity, relationship to study medication, date and day of onset, date and day of resolution, treatment given to treat the adverse event, action taken, the outcome, whether the event was an SAE, whether it led to withdrawal. Listings will be sorted by treatment sequence, participant identification number, onset date, SOC, and PT. If onset year is non-missing but month and/or date is missing, then the day of the most recent study drug dose will be imputed as onset date.

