## 1.2 Schedule of Activities (SoA)

 Table 1
 Schedule of Activities

	Screening		4-Way Crossover Period Visit 3-6						End of Study Evaluation 		
Procedures	Daytime V1	PSG V2	PSG V3	Wash- out 	PSG V4	Wash- out	PSG V5	Wash- out	PSG V6	Wash- out	
Trial Day (Visit Window)	Up to 4 w	veeks				Up to 8	weeks				2 weeks post V6 ± 3 days
Informed consent	X										
Non-PSG enrollment criteria	X										
Demography	X										
ESS	X										
Physical exam	X										
Medical history	X										
Clinical laboratory test	X										
Pregnancy test 	X										
12 Lead ECG	X										
PSG Exam		$X^4$	X		X		X		X		
Randomization 			X								
Administration of study treatment 			X		X		X		X		
DSST 			X		X		X		X		
Vital signs 	X	X	X		X		X		X		
AE/SAE monitoring			X	X	X	X	X	X	X	X	X
Prior/concomitant medication monitoring	X	X	X	X	X	X	X	X	X	X	X

Abbreviations: AE = adverse event; DSST = Digit Symbol Substitution Test; ECG = electrocardiogram; ESS = Epworth Sleepiness Scale; PSG = polysomnography; SAE = serious adverse event; WOCBP = women of childbearing potential.

<sup>1 Can be conducted remotely. For patients enrolling in Study APC-003-OLE, can be conducted concurrently with first visit of Study APC-003-OLE.

<sup>2 Each washout period is a minimum of 7 days

<sup>3 WOCBP only

<sup>4 A PSG conducted by the study site within 6 months that meets PSG enrollment criteria can take the place of a screening PSG and V2

<sup>5 Randomization occurs when participant meets enrollment criteria up to the time of the first crossover period

<sup>6 Study medication administered immediately before lights out

<sup>7 Administer at similar time after awakening after each crossover PSG, approximately 1 hour after awakening

<sup>8 Vital signs include the following: seated blood pressure, pulse, respiratory rate; vital signs on PSG nights taken after admission to PSG lab

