7.2.1. Treatment-emergent Adverse Events

A treatment-emergent adverse event (TEAE) is defined as any event not present prior to exposure of study drug or an event already present that worsens in either severity or frequency following exposure. Each TEAE is assigned to the most recent study treatment administered on or before the TEAE's date of onset.

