10. APPENDICES

10.1. Appendix A: Schedule of Activities

Procedures	Screening		4-Way Crossover Period Visit 3-6						End of Study Evaluation ¹	
	Daytime V1	PSG V2	PSG V3	Wash- out ²	PSG V4	Wash- out	PSG V5	Wash- out	PSG V6	Wash- out
Trial Day (Visit Window)	Up to 4 weeks		Up to 8 weeks						2 weeks post V6 ± 3 days	
Informed consent	X									
Non-PSG enrollment criteria	X									
Demography	X									
ESS	X									
Physical exam	X									
Medical history	X									
Clinical laboratory test	X									
Pregnancy test ³	X									
12 Lead ECG	X									
PSG Exam		X ⁴	X		X		X		X	
Randomization ⁵			X							
Administration of study treatment ⁶			X		X		X		X	
DSST ⁷			X		X		X		X	
Vital signs ⁸	X	X	X		X		X		X	
AE/SAE monitoring			X	X	X	X	X	X	X	X
Prior/concomitant medication monitoring	X	X	X	X	X	X	X	X	X	X

Abbreviations: AE = adverse event; DSST = Digit Symbol Substitution Test; ECG = electrocardiogram; ESS = Epworth Sleepiness Scale; PSG = polysomnography; SAE = serious adverse event; WOCBP = women of childbearing potential.

¹ Can be conducted remotely. For patients enrolling in Study APC-003-OLE, can be conducted concurrently with first visit of Study APC-003-OLE.

² Each washout period is a minimum of 7 days

³ WOCBP only

⁴ A PSG conducted by the study site within 6 months that meets PSG enrollment criteria can take the place of a screening PSG and V2

⁵ Randomization occurs when participant meets enrollment criteria up to the time of the first crossover period

⁶ Study medication administered immediately before lights out

⁷ Administer at similar time after awakening after each crossover PSG, approximately 1 hour after awakening

⁸ Vital signs include the following: seated blood pressure, pulse, respiratory rate; vital signs on PSG nights taken after admission to PSG lab

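### SAP 7.2.5's rule for partly missing adverse event onset dates has no reference date and ignores a known month or resolution date, so it can charge an event to a treatment taken afterwards

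*SAP*

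**What the plan says.** The rule is the last sentence of the listings paragraph in SAP 7.2.5: "If onset year is non-missing but month and/or date is missing, then the day of the most recent study drug dose will be imputed" as the onset. One rule covers a missing day, a missing month, or both.

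Other provisions that bear on it:

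- SAP 7.2.1 makes onset decide the treatment: "Each TEAE is assigned to the most recent study treatment administered on or before the TEAE's date of onset".
- SAP 7.2.5 tabulates by treatment: "For TEAEs, the following will be summarized by study treatment and presented for the Safety Set".
- The listing in the same paragraph as the rule includes "date and day of onset, date and day of resolution", so a resolution date is collected.
- On dose spacing, the Protocol 1.2 schedule says "Each washout period is a minimum of 7 days". The end-of-study evaluation is set at "2 weeks post V6 ± 3 days" (SAP Appendix A).
- SAP 7.2.5 covers "All AEs (serious and non-serious) occurring after completion of the informed consent process and before the end of study", whereas Protocol 7.3.1 starts collection at randomization.
- Protocol 4.1 and SAP 3.1 have events recorded at every visit and by telephone in each washout.
- SAP 4.4 rules out imputing missing data and makes no exception for event dates.

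**The concern.** Looking back for the latest dose needs a starting date. The natural one is the onset, but that is the missing value. The SAP names no substitute, such as the report date, the next visit or the end of study. The rule also sets aside information that the trial records. If only the day is unknown, the month is still known but unused, and a resolution date does not limit the imputed onset.

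In a parallel-group trial a misplaced onset would rarely change the treatment group. Here each participant takes four treatments, possibly a week apart, and SAP 7.2.1 reads the treatment off the onset date. A misplaced onset can therefore move an event from one treatment column to another, for example from placebo to AD109. It can also turn an event that began before the first dose into a treatment-emergent one.

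**Working it through.** The plan gives no figure to reproduce. The check is a reading of the rule, one worked example and a count of days.

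**Reading.** SAP 7.2.5 supplies no anchor, no month check and no resolution check, and no other section does so. The meaning closest to SAP 7.2.1, the latest dose before onset, is circular when onset is unknown.

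**Worked example (assumed dates).** Doses fall on 17, 24 and 31 March and 7 April 2021. An event truly begins on 20 March, in period 1. It is recorded as March 2021, day unknown, and resolved on 22 March. If the rule is read as the last dose received, onset becomes 7 April. That is outside the recorded month, 16 days after resolution, and charged to the period 4 treatment, taken 18 days after the event began. Nothing in the SAP blocks this result.

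**Count of onset days.**

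Inputs: four doses at the minimum spacing, on days 0, 7, 14 and 21 (Protocol 1.2). Follow-up runs to 14 days after the last dose (SAP Appendix A), so possible onset days are 0 to 35, which is 36 days. The correct treatment is the one SAP 7.2.1 would give with the true date.

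- *Last dose received in the study.* Days 0 to 20 precede the last dose and are charged to a later treatment: 21/36 = 58.3%.
- *Latest dose at the time of report, with the event recorded at the next PSG visit after that night's dose.* Days 0 to 20 are charged to the next treatment: 21/36 = 58.3%.
- *Latest dose at the time of report, with the report made before the next dose.* The imputed dose is the correct one every time: 0/36 = 0%.

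Sensitivity of the 58.3%:

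- Moving the end-of-study evaluation by 3 days either way gives 21/33 = 63.6% or 21/39 = 53.8%.
- With doses 14 days apart (days 0, 14, 28 and 42, onset days 0 to 56) it is 42/57 = 73.7%.

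**Conflict with a known month.** This used every start date in 2021 with each of the 36 onset days (365 × 36 = 13,140 combinations), only the day being missing. Under the last-dose-received reading, the imputed date falls in a month after the recorded one in 21.1% of combinations (47.9% with 14-day spacing). Under the report-after-next-dose reading the figure is 7.7%. These are assignments that the recorded month alone contradicts. A resolution date would contradict more, but the documents do not allow that share to be computed.

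**The case against.** The strongest reply is that the ordinary reading is harmless. A data manager would look back from the date the event was reported. With contact at each visit and by telephone in each washout, the report would usually come before the next dose, and the error is then zero. This stands as a likely practice, but the SAP does not state it. It is also not fully secure. Visits 3 to 6 are overnight stays with dosing at lights out and a test the next morning, so an event from the preceding washout can be recorded after that night's dose.

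A second reply is that the rule sits in a paragraph on listings and SAP 4.4 forbids imputation, so the imputed date may never reach the tables. The SAP does not say outright that the tables use it. However, SAP 7.2.1 needs an onset date to place any event under a treatment, and the listings are themselves grouped by treatment. The clash with SAP 4.4 is a further reason to edit the text.

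Third, a known month seldom identifies one of four weekly doses, so using it would not settle most cases. That is correct. It is an argument for flagging ambiguous events, not for accepting a date that the record contradicts.

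Fourth, the case of an event before the first dose is narrow. Protocol 7.3.1 starts collection at randomization, and the schedule marks randomization at the first dosing visit. It remains possible because the schedule's randomization footnote may allow earlier randomization and SAP 7.2.5 speaks of events from consent.

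Finally, partial dates should be few, SAP 7 makes the safety analyses descriptive, and no efficacy result depends on this. All of that stands.

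**Conclusion.** The rule is defective as written, and the consequence is minor. It lacks a reference date and disregards date parts and resolution dates that the trial collects. It can therefore produce an onset that the record contradicts and charge a treatment taken after the event. The share of possible onset days charged to a later treatment is between 0% and 58%, depending on an anchor the SAP leaves open. This assumes 7-day spacing and onset days 0 to 35. These shares describe the calendar and do not predict event rates. The number of partly dated events is not in the documents.

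A reader might infer that the rule sends every partly dated event to the period 4 treatment. That follows only if the rule means the last dose in the study, which the SAP does not say. A reader who counted only the 28 days from the first dose would also put the error at 21/28 = 75%. That leaves out most of the follow-up after the last dose, where the last-dose reading charges the right treatment. Nor do the documents support a claim that the by-treatment safety tables are materially distorted.

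The open anchor has one practical consequence. SAP 4.1 requires two independent programs to agree, so the programmers would have to choose an anchor that the plan does not specify.

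**What to change.** Replace the sentence in SAP 7.2.5 with a rule on these lines:

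1. Keep every known part of the onset date.
2. Impute the latest dose date that is consistent with those parts and not after the resolution date. Where the eCRF records when the event was first reported, the imputed date must also not be after that report.
3. If the month is known and no dose date meets step 2, use the first day of that month, so that SAP 7.2.1 assigns the preceding dose.
4. If the known parts place onset before the first dose, do not count the event as treatment-emergent.
5. Flag in the listing any event for which more than one treatment remains possible.
6. State that this rule is an exception to SAP 4.4.

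In the worked example, the latest dose in March that is not after 22 March is 17 March, which restores the event to period 1. With no resolution or report date, 31 March would be imputed and the event flagged. The rule removes assignments that the record contradicts, but it does not resolve every ambiguous one.

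The cost is minor SAP wording and programming work. The sponsor should first confirm whether the eCRF holds a first-report date for each event, because the variables listed in SAP 7.2.5 do not include one. The rest of the rule works without it.

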7.3. Vital Signs

Vital sign data will be summarized by presenting descriptive statistics of actual values and changes from baseline by study treatment. Vital sign parameters include respiratory rate, temperature, systolic blood pressure, diastolic blood pressure, and heart rate. A by-participant listing of vital signs will also be provided.

7.4. DSST

A repeated measures model (see Section 4.7) will be used to model the natural log of total number of the correct symbol assignments¹ (log (total completed - total incorrect)) from the DSST.

Exponentiation of the model-based LS mean estimates of log values will be used to provide the following:

- Geometric mean of DSST by study treatment (AD109, placebo, R-oxybutynin, and atomoxetine), and
- Ratio of (geometric) mean of DSST between AD109 and the other three treatments (placebo, R-oxybutynin, and atomoxetine) with the 95% confidence intervals.

Descriptive statistics of DSST and a by-participant listing (with both raw values and natural log of total complete) will also be provided.

7.5. PSG Parameters

PSG safety data will be summarized by presenting descriptive statistics of actual values and changes from baseline by treatment. PSG safety parameters include total sleep time, heart rate, and total time with $\text{SaO}_2 < 90\%$. A by-participant listing of PSG parameters (including baseline and efficacy parameters) will also be provided.

8. INTERIM ANALYSIS

No formal interim analysis is planned.

9. SAMPLE SIZE AND POWER CALCULATIONS

A total of 58 patients will enter the 4-treatment crossover study. The study will have 80% power to detect a treatment difference at a two-sided 0.05 significance level, if the true difference between treatments on HB is at least -3.7 %min/h. This assumes that the within-participant

¹ In the case that the total correct is 0, the participant will be dropped from the model.

standard deviation is 9, estimated from Study APN-006, and that the discontinuation rate is less than 20%.

10. APPENDICES

10.1. Appendix A: Schedule of Activities

Procedures	Screening		4-Way Crossover Period Visit 3-6						End of Study Evaluation ¹	
	Daytime V1	PSG V2	PSG V3	Wash- out ²	PSG V4	Wash- out	PSG V5	Wash- out	PSG V6	Wash- out
Trial Day (Visit Window)	Up to 4 weeks		Up to 8 weeks						2 weeks post V6 ± 3 days	
Informed consent	X									
Non-PSG enrollment criteria	X									
Demography	X									
ESS	X									
Physical exam	X									
Medical history	X									
Clinical laboratory test	X									
Pregnancy test ³	X									
12 Lead ECG	X									
PSG Exam		X ⁴	X		X		X		X	
Randomization ⁵			X							
Administration of study treatment ⁶			X		X		X		X	
DSST ⁷			X		X		X		X	
Vital signs ⁸	X	X	X		X		X		X	
AE/SAE monitoring			X	X	X	X	X	X	X	X
Prior/concomitant medication monitoring	X	X	X	X	X	X	X	X	X	X

Abbreviations: AE = adverse event; DSST = Digit Symbol Substitution Test; ECG = electrocardiogram; ESS = Epworth Sleepiness Scale; PSG = polysomnography; SAE = serious adverse event; WOCBP = women of childbearing potential.

¹ Can be conducted remotely. For patients enrolling in Study APC-003-OLE, can be conducted concurrently with first visit of Study APC-003-OLE.

² Each washout period is a minimum of 7 days

³ WOCBP only

⁴ A PSG conducted by the study site within 6 months that meets PSG enrollment criteria can take the place of a screening PSG and V2

⁵ Randomization occurs when participant meets enrollment criteria up to the time of the first crossover period

⁶ Study medication administered immediately before lights out

⁷ Administer at similar time after awakening after each crossover PSG, approximately 1 hour after awakening

⁸ Vital signs include the following: seated blood pressure, pulse, respiratory rate; vital signs on PSG nights taken after admission to PSG lab

